Long-Term Effects of COVID-19 in Adolescents (LoTECA)

Study protocol

NCT 04686734

Date: 4th of January, 2021

Project description

1. State of the art, knowledge needs and project objectives

The Coronavirus Disease 2019 pandemic has high mortality; in general, children are mildly affected

The Coronavirus Disease 2019 (COVID-19) pandemic, caused by Severe Acute Respiratory Syndrome Coronavirus 2 (SARS-CoV-2), is a tremendous threat to human health and welfare worldwide.⁵⁵ The clinical presentation varies from asymptomatic infection over mild upper respiratory tract illness to severe viral pneumonia causing Acute Respiratory Distress Syndrome (ARDS) and respiratory failure; old age and chronic cardiovascular morbidity are important risk factors for severe outcome.⁵⁶

Evidence suggests that previously healthy children are usually mildly affected by SARS-CoV-2 in the acute phase. A nation-wide retrospective study in China including 2143 children with COVID-19 reported “severe” or “critical” disease among 6 % only; age < 1 year was a risk factor.¹³ Two other Chinese studies of hospitalized children during the height of the pandemic in the city of Wuhan showed excellent recovery in the great majority, and only one death.^{29,32} Corroborating these results, statistics from the outbreak in Italy report only 1.2% COVID-19 cases and no deaths < 18 years of age.³⁰

Long-lasting complications to COVID-19 in children might be development of post-infectious chronic fatigue and chronic fatigue syndrome

Despite the relatively mild clinical presentation of COVID-19 in children, the long-lasting medical effects of is unknown at the moment. However, as fatigue seems to be a prominent symptom of COVID-19 infection,¹³ it is conceivable – and in line with preliminary reports - that post-infectious chronic fatigue (PICF) might develop in vulnerable individuals, of which a subgroup may fulfill diagnostic criteria for the Chronic Fatigue Syndrome (CFS). PICF/CFS is a well-known sequel of several other infections, such as Epstein-Barr virus (EBV).^{17,22} Normally, increased load of the infectious agent is not reported in PICF/CFS.^{5,25} The underlying causes remain elusive; however, autoimmunity is a possible mechanism. The most consistent immune alteration is a tendency towards low-grade systemic inflammation, as reflected in significantly elevated serum C-reactive protein (CRP),^{25,53} elevated pro-inflammatory cytokines,^{24,39} and increased levels of innate immunity gene products in whole blood gene expression analyses.⁴¹ Alternatively, immune disturbances might be a side-effect which is not causally involved in PICF/CFS symptoms and disabilities. Recent neurobiological studies suggest that PICF/CFS is related to misguided automatic and unconscious predictions.^{26,54} This alternative model is supported by evidence of psychosocial factors (such as negative life events and trait negative affectivity) being risk factors for long-lasting post-infectious conditions.

PICF/CFS is a significant health problem among adolescents: Disability is often severe, treatment options are limited, and there is a strong negative impact upon academic development, social security systems, and family networks.¹⁹ The societal costs are correspondingly large.⁴⁷ The present pandemic provides a unique opportunity to further scrutinize the disease mechanisms underlying PICF/CFS in children.

COVID-19 is associated with inflammatory enhancement; a “cytokine storm” might contribute to development of respiratory failure

At a gross level, the immunological host response to SARS-CoV-2 is characterised by increased levels of circulating proinflammatory cytokines; this inflammatory enhancement, which might escalate towards a “cytokine-storm”, is thought to contribute significantly to tissue damage and clinical deterioration, including severe pulmonary pathology and ARDS.^{8,46,58}

Interestingly, SARS-CoV infection is also associated with a delayed expression of type I interferon (IFN) signaling, which is a crucial part of the innate defense against viral infections.³⁶ Type I IFN signaling is initiated by pattern recognition receptors (such as the Toll-like receptors) in responses to viral nucleic acid; the subsequent intracellular cascade promotes the synthesis of type I interferons (IFNs), which in turn activate the JAK-STAT signal pathway promoting the expression of IFN-stimulated genes (ISGs).⁴⁰ One effect of this signaling cascade is increased transcription of the APOBEC3-family of deoxycytidine deaminases that counteract a broad range of retroviruses, including coronaviridae.^{2,38} The net result is a limitation of virus spread. The N protein of SARS-CoV seems to antagonize the type I interferon (IFN) signaling by interacting with the pattern recognition receptors, thereby enabling the virus to escape this host response;³³ other viral mechanisms might contribute as well.⁸

This “escape capability” might explain important features of COVID-19 infection as well, such as the rapid viral replication rate in infected individuals, which in turn might contribute to tissue pathology.²⁸ In addition, it has been hypothesized that this viral IFN antagonism plays a crucial part in promoting the “cytokine storm” in SARS-CoV infection.⁷ The delayed type I IFN signaling promotes the accumulation of pathogenic inflammatory monocyte-macrophages (IMMs), which in turn are responsible for increased cytokine levels as well as direct lung tissue damage and inhibition of virus-specific T cell responses. Thus, a detailed mapping of the initial innate responses to SARS-CoV-2 might provide a clue towards better understanding of two separate causes of tissue damage, which over time might amplify each other in a vicious circle: The direct cytotoxic effect of the virus as well as the immunopathologies resulting from uncontrolled inflammatory enhancement.

This study aims to study long-term effects in adolescent COVID-19, in particular development of chronic fatigue

The overarching objective for this prospective cohort study on COVID-19 in adolescents is to study the long-term effects, with particular emphasis on post-infectious chronic fatigue. We hypothesise that children having undergone COVID-19 has a higher prevalence of PICF/CFS long after the acute infectious event; furthermore, that risk factors for PICF/CFS encompass a complex mixture of genetic vulnerability and psychosocial factors.

2. Material and methods

The design allows prospective as well as cross-sectional analyses

Adolescents (12-25 years) with confirmed SARS-CoV-2-infection are eligible for the present study (Table 1, Fig. 2). Inclusion will be based on informed consent from patients/next-of-kin. We assume a total number of 500 included cases. A follow-up control is scheduled 6 months after inclusion. This design enables prospective and cross-sectional analyses.

Risk factors for long-term complications will be analysed using regression modelling. Fatigue is defined as the primary endpoint. This sensation is operationalized using the Chalder Fatigue Questionnaire, which is known to have good validity and reliability in children.⁶ Relevant independent (explanatory) variables include (but are not restricted to):

- *Background:* Sex, age, ethnicity, previous medical history, smoking habits in family, presence of allergy/atopy, etc.
- *Initial clinical findings:* Symptom load/intensity, fever, routine blood haematology and biochemistry, etc.
- *Infectious load:* SARS-CoV-2 viral counts.
- *Immune function:* Increased general inflammation
- *Genetic predisposition:* Cf. below (Tab. 2) for a comprehensive list of candidate genetic markers
- *Questionnaire results:* Emotionality (depression/anxiety, emotional awareness), personality factors (neuroticism, worrying), perceived loneliness, and negative life events.
- *Autonomic cardiovascular control:* Increased sympathetic nervous activity, decreased parasympathetic nervous activity
- *Cognitive functions:* Increased verbal memory, attention bias towards disease-related words, reduced working memory

[figure not shown]

Table 1. Criteria for inclusion and exclusion**Inclusion criteria**

Positive SARS-CoV-2 test
 Age 12-25 years
 < 28 days since onset of first symptom

Exclusion criteria

Hospitalised because of COVID-19
 Pregnancy
 Lack of consent from patient/next-of-kin

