- *Biobanking:* Biobanking of blood samples (whole blood, plasma, serum, RNA, viable Peripheral Blood Mononuclear Cells (PBMC)) as well as urine, hair and fecal samples, for subsequent analyses (cf. below). Blood sampling will be obtained in a fixed sequence from antecubital venous puncture.

- *Questionnaire:* A composite questionnaire will chart clinical symptoms, as well as background, psychological and social variables, and will be used for diagnostic categorization according to different case definitions of CFS/ME. The Chalder Fatigue Questionnaire (CFQ) charts subjective experience of physical and mental fatigue, and has been extensively used in CFS research. In this study, the CFQ total linear score (i.e. the sum across all 11 items, each item scored on a zero to three Likert scale) is applied as the primary endpoint in prediction modelling. Furthermore, fatigue caseness is defined as a CFQ total dichotomous score of 4 or higher (each item scored 0-0-1-1). The Hospital Anxiety and Depression Scale (HADS) is a validated questionnaire for charting symptoms of depression and anxiety. It consists of 14 items rated zero to three on Likert scales, allowing computation of sub-scores for depression and anxiety symptoms. In the present study, these sub-scores as well as total sum score will be applied. The Life Event Checklist (LEC) is a validated questionnaire for assessing both positive and negative life events. The inventory lists 45 events; the respondents are asked to mark each of them as positive or negative, and grade their impact on four-point Likert scales. The Brief Pain Inventory (BPI) is a validated questionnaire for assessing pain. In this study,

the four BPI items assessing pain severity on ten-point Likert scales will be used to compute a total sum score; in addition, scores on a single item (average pain) will be reported. Cf. supplement for further information on questionnaire instruments.

- *Autonomic cardiovascular control*: A 5-minute ECG recording will be performed applying The Bittium Faro 360® device (Bittium Corporation, Oulu, Finland), enabling later heart rate variability analyses. In the frequency-domain, vagal (parasympathetic) activity is the main contributor to high-frequency (HF) variability of heart rate, whereas both vagal and sympathetic activity contributes to low-frequency (LF) variability. The LF/HF ratio is considered an index of sympathovagal balance.

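### The first hypothesis claims a higher prevalence of PICF/CFS after COVID-19, but no comparator is named and only infected persons are enrolled; reword it as estimation or name the comparator in advance

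*Protocol*

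**What the plan says.** The objectives at the end of Section 1 contain two hypotheses. The first is comparative: "We hypothesise that children having undergone COVID-19 has a higher prevalence of PICF/CFS long after the acute infectious event". The second, in the same sentence, concerns genetic and psychosocial risk factors.

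Section 2 (Material and methods) fixes who is studied. Persons aged 12-25 "with confirmed SARS-CoV-2-infection are eligible for the present study", and the planned size is given as: "We assume a total number of 500 included cases". The first inclusion criterion in Table 1 is "Positive SARS-CoV-2 test"; another is "< 28 days since onset of first symptom". Table 1 excludes persons hospitalised because of COVID-19 and pregnant persons. The follow-up control at 6 months is a visit, not a control group.

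On analysis, Section 2 says: "Risk factors for long-term complications will be analysed using regression modelling". The primary endpoint is the CFQ total linear score, used in prediction modelling. The section on power estimation and statistical analyses expects about 10% of participants to meet CFS definitions at 6 months. It takes that rate from earlier post-infective studies and projects about 50 patients for cross-sectional analyses.

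**The concern.** A claim of higher prevalence needs two rates, and the plan produces one. Nothing in the text shown names an uninfected group, a population prevalence or a historical cohort as the second.

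The stake is what the 6-month figure will be taken to mean. Section 2 lists loneliness, negative life events and depression/anxiety among the explanatory variables for fatigue. Uninfected adolescents can have these too, so a one-group prevalence does not separate the effect of the virus from fatigue that would have been present anyway. The section on stakeholders aims the results at policy makers and the general public as well as scientists. An unsupported *higher* would therefore reach readers who are unlikely to ask about the comparator.

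**Working it through.** **1. Can anything in the document serve as comparator?**

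| Candidate | Where | Why it does not serve |
|---|---|---|
| Uninfected participants | Section 2, Table 1 | A positive test is required |
| The 10% CFS rate | Power considerations | Expected rate in this cohort, from post-infective studies; as the reference it would equal the expected result |
| COFFI cohorts | Section 3, national network and COFFI | Themselves post-infection cohorts, cited as network and infrastructure |
| Participants' own baseline | Section 2, Table 1 | Inclusion is within 28 days of first symptom, so baseline falls in or soon after the acute illness |
| Cross-sectional work on about 50 CFS patients | Power considerations | Drawn from the infected cohort |

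**2. The protocol's own figure.** 500 × 0.10 = 50, as stated.

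**3. What the cohort can deliver.** Wilson 95% interval with p = 0.10, n = 500, z = 1.96 (z² = 3.8416):

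- centre = (p + z²/2n) / (1 + z²/n) = (0.1 + 0.0038416) / 1.0076832 = 0.1031
- half-width = z·√(p(1−p)/n + z²/4n²) / (1 + z²/n) = 1.96·√(0.00018 + 0.00000384) / 1.0076832 = 0.0264
- interval = 7.7% to 12.9%

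If only 400 were evaluable (an assumption; the protocol gives no loss rate), 40/400 gives 7.4% to 13.3%.

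**4. How far the answer depends on the missing comparator.** Every reference rate and reference size here is an assumption, because the protocol gives none. The true rate is set at 10% in 500 infected persons.

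*Fixed external reference p₀.* Exact binomial test: reject at the smallest count r with P(X ≥ r | 500, p₀) ≤ 0.025; power = P(X ≥ r | 500, 0.10).

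| p₀ | r | Power |
|---|---|---|
| 5% | 36 | 98.8% |
| 7% | 48 | 63.9% |
| 8% | 53 | 34.8% |

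*Reference estimated in 500 persons* (two proportions, pooled null, normal approximation, two-sided 5%). At 5%:

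- null SE = √(0.075·0.925·2/500) = 0.01666
- alternative SE = √((0.09 + 0.0475)/500) = 0.01658
- power = Φ((0.05 − 1.96·0.01666)/0.01658) = Φ(1.05) = 85%

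At 7% the same formula gives 40%. Whether 500 infected persons are enough therefore depends on a reference that is not named.

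**5. The other hypothesis.** For 50 CFS against 450 others, taking d = 0.5 as a medium effect: power = Φ(0.5/√(1/50 + 1/450) − 1.96) = Φ(3.354 − 1.96) = 92%. The protocol's remark on medium effects is reasonable for within-cohort comparisons. It does not bear on the prevalence hypothesis.

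**The case against.** A reader might infer that this study can never show a higher prevalence. The documents do not support that. The limit holds for this cohort alone: step 4 shows that the same 500 persons, under the same Table 1, would have ample power against a sufficiently low external reference. A statistical analysis plan, not shown here, could specify one. What stands is that the hypothesis belongs to the protocol and is incomplete there, and that no analysis of the enrolled cohort by itself can supply a rate without infection.

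Fig. 2 is cited beside Table 1 and is not shown. Nothing is concluded about its content.

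A reader might also extend the point to a missing case definition. The protocol speaks of several definitions of CFS/ME, and its one cut-off ("fatigue caseness is defined as a CFQ total dichotomous score of 4 or higher") carries no duration. That is a separate matter and largely one for the analysis plan. The supplement lists instruments for CFS diagnosis and post-exertional malaise, and the CFQ is given at baseline and at 6 months. It matters here only because any comparison needs the same definition on both sides.

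Finally, the consequence is limited. The primary endpoint and the risk-factor hypothesis need no uninfected group, no prevalence test is described, no attribution claim is stated, and negative findings are to be reported. All of this is fair. It narrows the point to one stated hypothesis, which the plan as written still cannot answer.

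**Conclusion.** The point holds in this form: the text shown names no comparator for the first hypothesis, eligibility admits only infected persons, and the 10% figure is an expected post-infective rate. The enrolled cohort alone can estimate prevalence, about 10% with a 95% CI of 7.7% to 12.9% if the protocol's expectation is met and all 500 are evaluable. It cannot test *higher* or support attribution to the virus without an external or added comparator.

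The interval rests on the protocol's figures. The power values rest on assumed reference rates and sizes, and show only how strongly the answer depends on them. It would be too strong to conclude that the study as a whole fails for want of controls. This should be fixed, but it does not threaten the primary analysis.

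**What to change.** **Default.** Replace the first hypothesis with an estimation objective: to estimate, with 95% CI, the 6-month prevalence of PICF and of CFS among persons aged 12-25 with a positive SARS-CoV-2 test, not hospitalised for COVID-19 and not pregnant, included less than 28 days after first symptom. State that no claim of higher prevalence will be made from this cohort alone. The population wording matters, because Table 1 does not cover all infected persons aged 12-25. The change costs text only, with no change to Table 1 or N; the downside is that the comparative claim is given up.

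**If the comparative claim is kept,** name the comparator in advance.

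- *External reference.* A prevalence with the same case definition, age range and calendar period, with its sampling error included in the test. Table 1 and N stay as they are. The cost is finding a reference that truly matches; if none exists, the claim cannot be kept this way.
- *Concurrent uninfected group (optional, costlier).* It needs its own eligibility criteria and index date, since a positive test and time from first symptom cannot apply, and the same 6-month programme. This means an amendment, consent and a justified size. With 100 controls added (600 in all), power by the step 4 formula would be 32% at an assumed uninfected rate of 5%. Moving 100 of the 500 places to controls would instead cut expected CFS cases from 50 to 40 and widen the interval to 7.4% to 13.3%.

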- *Biobanking:* Biobanking of blood samples (whole blood, plasma, serum, RNA, viable Peripheral Blood Mononuclear Cells (PBMC)) as well as urine, hair and fecal samples, for subsequent analyses (cf. below). Blood sampling will be obtained in a fixed sequence from antecubital venous puncture.

- *Questionnaire:* A composite questionnaire will chart clinical symptoms, as well as background, psychological and social variables, and will be used for diagnostic categorization according to different case definitions of CFS/ME. The Chalder Fatigue Questionnaire (CFQ) charts subjective experience of physical and mental fatigue, and has been extensively used in CFS research. In this study, the CFQ total linear score (i.e. the sum across all 11 items, each item scored on a zero to three Likert scale) is applied as the primary endpoint in prediction modelling. Furthermore, fatigue caseness is defined as a CFQ total dichotomous score of 4 or higher (each item scored 0-0-1-1). The Hospital Anxiety and Depression Scale (HADS) is a validated questionnaire for charting symptoms of depression and anxiety. It consists of 14 items rated zero to three on Likert scales, allowing computation of sub-scores for depression and anxiety symptoms. In the present study, these sub-scores as well as total sum score will be applied. The Life Event Checklist (LEC) is a validated questionnaire for assessing both positive and negative life events. The inventory lists 45 events; the respondents are asked to mark each of them as positive or negative, and grade their impact on four-point Likert scales. The Brief Pain Inventory (BPI) is a validated questionnaire for assessing pain. In this study,

the four BPI items assessing pain severity on ten-point Likert scales will be used to compute a total sum score; in addition, scores on a single item (average pain) will be reported. Cf. supplement for further information on questionnaire instruments.

- *Autonomic cardiovascular control*: A 5-minute ECG recording will be performed applying The Bittium Faro 360® device (Bittium Corporation, Oulu, Finland), enabling later heart rate variability analyses. In the frequency-domain, vagal (parasympathetic) activity is the main contributor to high-frequency (HF) variability of heart rate, whereas both vagal and sympathetic activity contributes to low-frequency (LF) variability. The LF/HF ratio is considered an index of sympathovagal balance.
- *Spirometry*: The EasyOne Air® spirometer device (NDD Medical Technologies, Andover, Massachusetts, USA) is used to obtain standard ventilation variables.
- *Cognitive functions*. Participants are exposed to the Hopkins Verbal Learning Test-Revised (HVLT-R), assessing verbal learning, delayed recall, and recognition; the Digit Span forward and backward test, assessing working memory; an Attention Bias test of automatic biases towards disease-associated words; and the Function Acquisition Speed Test assessing cognitive fusion.

Ahus will host the biobank and database for the present study.

Considerations on power estimation and statistical analyses

The novelty of COVID-19 and the lack of comparable studies among adolescents precludes a formal power analyses. However, it should be noted that a prospective cohort of 500 patients is comparable to similar cohort studies in the field. Based upon previous post-infective studies, about 10 % of included patients will adhere to diagnostic definitions of CFS after 6 months; in the present study, that will leave about 50 patients for cross-sectional analyses, which is also considered sufficient to detect at least medium effect sizes.

All statistical analyses are carried out with SPSS statistical software, and a $p < 0.05$ are considered statistically significant. Missing values are to be handled by multiple imputation techniques.

Ethics

Participation is based upon informed consent, and thorough information will be provided orally as well as in writing to the participants and (if younger than 16 years) to their parents/next-of-kin. All data will be treated and stored without personal identifying information, and in accordance with national directives. Generally, investigational methods are neither harmful nor painful (local anaesthetic ointment will be given prior to venous puncture).

Gender perspectives

Severe COVID-19 appears to be more common in males than in females.⁵⁶ Post-infectious complications, however, such as PICEF/CFS, are more common among females than males, the ratio being about 3:1. Thus, such complications strongly impact on women's health, but have traditionally received low attention. In this project, possible gender differences will be scrutinized in the analyses.

The projects benefits from a strong relationship to well-established research networks

The projects builds upon two collaborating networks that have been firmly established through previous research project: a) An international consortium of researchers on post-infectious complications (Collaborative of Fatigue Following Infection, COFFI), encompassing highly reputed research groups from six countries (US, UK, Australia, New Zealand, The Netherlands and Norway), and with the lead co-PI of this proposal as the chair of the consortium; b) An in-house collaborative with the EpiGen Molecular Research Laboratory and the Dept. of Microbiology, which are equipped with state of the art technology and manages the local biobank facilities. There are several co-publications within all these networks already.

The present project will guide clinical care and priorities in acute disease, contribute to development of therapeutics and prophylaxis, and help understand mechanisms behind long-term complications

The on-going COVID-19 pandemic represents a global threat towards health and welfare. The present project aims to mitigate some of the detrimental consequences. First and foremost, it will provide increased knowledge on long-term effects including a better understanding of PICEF/CFS and other sequels, and might guide clinical services and development of prophylactic measures. To the best of our knowledge, no similar study on adolescents has been performed – or is ongoing – at present.

Primary and secondary stakeholders

Given the seriousness of COVID-19 infections and the urgent need for scientific knowledge, rapid and continuous dissemination of project results will receive high attention. The target for dissemination is not restricted to the scientific community, but includes a wide range of health-care workers, politicians, policy makers, health care administrators, and the general public.

Results will be disseminated widely; scientific dissemination is prioritized

Several means of dissemination will be exploited, including scientific papers; popular science newspaper articles; giving interviews; meetings with politicians, public health providers and other stakeholders; social media. Dissemination to researchers and the scientific community includes publications in international, peer-reviewed medical journals. The main results will be offered to journals of high impact. Negative findings will also be reported.

3. Implementation

Research group, project managers, and in-house resources

The present project is hosted by the PAEDIA research group at Akershus University Hospital (Ahus), which has extensive experience in translational immunology as well as clinical research, and a strong track record of result dissemination and implementation. The group has established a well-working infrastructure for patient flow and data acquisition, and a large collaborative network with national and international experts on various methodological aspects.

The PAEDIA research group is headed by [name], who is also the PI of the present project, and Chair of the COFFI collaboration. [name] is the most published and cited PICF/CFS researcher in Norway. Other members of PAEDIA include two postdoctoral fellows, six PhD fellows, two master students, and three clinical consultants. The local research support staff consists of one laboratory engineer, two research nurses and two research secretaries. An internal learning program for PhD fellows has been established, encompassing a) one-to-one supervision sessions; b) regular in-group discussions; c) invited lecturers; d) oral presentation training and practice; e) seminars on selected topics (statistics, ethics). A total of five PhD fellows have successfully graduated over the past four years.

PAEDIA's primary collaborating unit at Ahus is the EpiGen Molecular Research Laboratory, headed by prof. [name], which is equipped with state of the art technology and manages the local biobank facilities. Profs. [name] and [name] have collaborated closely for several years, enjoying complementary expertise and ensuring a translational perspective.

National collaborative network and the COFFI collaborative

Over the last decade, [name] has established a multidisciplinary national scientific collaborative network, covering a large area of expertise. Several co-publications exist. For the present project, the collaboration with Profs. [name] and [name] at Oslo University hospital provides expertise in basic and applied immunology, the collaboration with Prof. [name] provides expertise in molecular immunology.

The COFFI consortium was founded by principle investigators following 12 post-infection cohorts in six countries.²¹ As of March 2019, the consortium is chaired by [name]; basic infrastructure (data managing, biobanking, statistical support) has been established, and will be made available for the present project.

Important measures to ensure integration between all collaborators encompass a) Shared responsibility for PhD supervision, b) Regular meetings (video link for international partners) to discuss scientific and strategic challenges; c) Hosting of seminars; and d) Face-to-face meetings.

Infrastructure and activities

Necessary research infrastructure is primarily related to a) immunological and molecular laboratory facilities, b) biobanking facilities, and c) data management facilities. All these facilities are available through the established collaborative networks, in particular the COFFI collaborative which is already hosted at Ahus.

Personnel and funding

Study personnel (paediatrician, research nurse and research secretary) necessary for initiation of the study and primary data acquisition is available within the PAEDIA research group. For data analyses, writing of papers, etc. a full-time PhD fellow will be needed, and funding will be sought from relevant funding institutions during the coming months. Other running costs in the project will be covered by the Section for Research and Development at Dept. of Pediatrics, Ahus.

An advisory board of two user representatives is the most important user involvement

For the present project, an advisory board of users will formally established, consisting of a) One representative from the “Youth council” at Ahus, consisting of adolescents suffering from chronic disorders; and b) One representative from the organization Recovery Norway, consisting of individuals having recovered from post-infectious chronic fatigue and similar conditions. The advisory board will meet quarterly with the PI; important themes for discussions are results’ interpretation and practical impact, ethical issues, considerations regarding further research, and dissemination/implementation strategies.

4. References

1. Alhogbani T. *Ann Saudi Med* 2016;36:78-80.
2. Barrett BS, et al. *Retrovirology* 2017;14:25.
3. Beidas M, et al. *Intervirol* 2018;61:30-5.
4. Bi Q, et al. *MedRxiv* 2020; DOI 10.1101/2020.03.03.20028423
5. Cameron B, et al. *J Med Virol* 2010;82:1684-8
6. Chalder T, et al. *J Psychosom Res* 1993;37:147-53
7. Channappanavar R, et al. *Cell Host Microbe* 2016;19:181-93.
8. Channappanavar R, et al. *Semin Immunopathol* 2017;39:529-39.
9. Chen D, et al. *Emerg Microbes Infect* 2019;8:1511-23.
10. Chen Y, et al. *Lancet* 2020; March 23.
11. Cui Y. *J Infect Dis* 2020; DOI 10.1093/infdis/jiaa113.
